7.4. Data sources

The analysis will be based on administrative data from MDV Co. Ltd., a longitudinal database based on health insurance claims and medical records obtained from the hospitals in which the DPC payment system for utilization of both inpatient and outpatient hospital claims (percentage of inpatients is about 45%). The database provides claims data from 314 hospitals (as of June 2017) using the DPC system for medical service claims (21% of general hospitals but 55% of general beds in Japan is under the DPC system) including approximately 14 million patient data.

7.5. Study size

All eligible patients are extracted from the database and used for the analysis. In the previous study (CER2; conducted based on the data from March 1st, 2011 to December 31st, 2017 for apixaban, edoxaban and warfarin), 14,830 patients on warfarin, 16,176 patients on apixaban and 4,438 patients on edoxaban were eligible for the analysis. The required number of patients for the planned analysis and the estimated number of eligible patients for each cohort is shown in a Statistical Analysis Plan

<Eliquis>

<B0661120> Safety and effectiveness evaluation of patients with non-valvular atrial fibrillation treated with OACs: Comparison between NOACs and warfarin (CER3)

<Final ver.1.1><20180508>

(SAP).

7.6. Data management

Data will be securely provided by MDV Co. Ltd. All analyses will be conducted using SAS software (Version 9.0 or higher, SAS Institute, Cary, NC, USA) with study results presented in Microsoft Excel tables.

7.7. Data analysis

Baseline patient demographic information will be compared among the warfarin and NOACs cohorts by appropriate tests (e.g., t-test, Mann Whitney-U test, chi-square test) based on the distribution of the measures. A PSM method will be used to balance patient characteristics between compared cohorts (apixaban versus warfarin, dabigatran versus warfarin, edoxaban versus warfarin or rivaroxaban versus warfarin). In addition to the simple PSM (that is, without “weighting”), a stabilized inverse probability treatment weighting (IPTW) method will be also used to balance patient characteristics between groups¹¹ (see also *Statistical Analysis Plan*). Cox proportional hazards models (OAC treatment as a single variable) will be used to calculate the hazard ratios with 95% confident intervals. Anticoagulant type (apixaban or warfarin, dabigatran or warfarin, edoxaban or warfarin or rivaroxaban or warfarin) was included and no other covariates were included in the COX model because two cohorts were balanced after propensity score matching.

Detailed methodology for summary and statistical analyses of data collected in this study will be documented in a SAP, which will be dated, filed and maintained by the sponsor. The SAP may modify the plans outlined in the protocol; any major modifications of primary endpoint definitions or their analyses would be reflected in a protocol amendment.

7.8. Quality control

This study is a retrospective analytical study using quality controlled data in a pre-existing database, and primary data collection will not be conducted. As for the data provided, quality of the data is guaranteed by MDV Co. Ltd., which has professional teams specialized in the maintenance and improvement of data quality. All of these processes are consistently managed in-house. All of operations for data management in MDV Co. Ltd. are conducted in accordance with standard operational procedures of MDV Co. Ltd...

Data analysis will be conducted by Crecon Medical Assessment Inc. (Tokyo, Japan). The final results will be quality checked internally by Crecon Medical Assessment according to their internal procedures. For quality assurance of analysis, they will conduct code review of all modules of program, descriptive statistics review of all variables and patients row data examination of all output results in a test phase.

7.9. Limitations of the research methods

1) Identification of NVAF, bleeding, stroke, TIA and SE events will be based on insurance claims data, and there is no medical record review to adjudicate these diagnosis, which may subject the

<Eliquis>

<B0661120> Safety and effectiveness evaluation of patients with non-valvular atrial fibrillation treated with OACs: Comparison between NOACs and warfarin (CER3)
<Final ver.1.1><20180508>

study of misclassification bias. 2) There is no information about the therapeutic range of warfarin therapy or INR monitoring results, which are important factors related to the safety and efficacy of warfarin treatment. In Japan, it has been pointed out that coagulation status is often sub-optimally controlled by warfarin in NVAF patients. 3) This is an observational study and patients with different treatments may be incomparable. These differences may impact the comparison between treatment groups. In this study, a PSM method or IPTW with stabilized weights will be used to make well matched cohorts. Although the cohorts are matched, some differences in patient background which are neither available from the database nor included in matching score might still affect the results.

7.10. Other aspects

Not applicable.

8. PROTECTION OF HUMAN SUBJECTS

8.1. Patient Information and Consent

The MDV database is comprised of unlinkable anonymized data. According to the ethical guidelines for epidemiological studies in Japan, informed consent is not always required for studies by unlinkable anonymized data.

8.2. Patient withdrawal

Not Applicable.

8.3. Institutional Review Board (IRB)/Independent Ethics Committee (IEC)

Since the MDV database is comprised of unlinkable anonymized data, IRB/IEC approval is not required.

8.4. Ethical Conduct of the Study

Not Applicable.

9. MANAGEMENT AND REPORTING OF ADVERSE EVENTS/ADVERSE REACTIONS

This study only includes data that already exist as structured data in an electronic database. In the data sources (MDV Co. Ltd.), it is not possible to link (i.e. identify a potential association between) a particular product and medical event for any individual. Thus, the minimum criteria for reporting an adverse event (i.e., identifiable patient, identifiable reporter, a suspect product, and event) are not available and unprojected adverse events are not reportable as individual adverse event reports.

<Eliquis>

<B0661120> Safety and effectiveness evaluation of patients with non-valvular atrial fibrillation treated with

OACs: Comparison between NOACs and warfarin (CER3)

<Final ver.1.1><20180508>

10. PLANS FOR DISSEMINATING AND COMMUNICATING STUDY RESULTS

All final data will be shared with BMSKK/BMS. It is also anticipated that results from this study will generate at least one study abstract for submission to a medical conference and one manuscript for submission to an international peer-reviewed journal. The appropriate conferences and journal will be decided upon by the alliance medical team. Abstract, presentation materials (poster or slide deck) or a manuscript will be reviewed and approved both by Pfizer and BMS

11. COMMUNICATION OF ISSUES

In the event of any prohibition or restriction imposed (e.g., clinical hold) by an applicable Competent Authority in any area of the world, or if the investigator is aware of any new information which might influence the evaluation of the benefits and risks of a Pfizer product, Pfizer should be informed immediately.

13. LIST OF TABLES

[Table 1. Demographic and clinical information of patients](#)

14. LIST OF FIGURES

None.

15. ANNEX 1. LIST OF STAND ALONE DOCUMENTS

None.

16. ANNEX 2. ENCEPP CHECKLIST FOR STUDY PROTOCOLS

None

1 AMENDMENTS FROM PREVIOUS VERSION(S)

Not applicable (first version, no amendments).

2 INTRODUCTION

Note: in this document any text taken directly from the Non-Interventional (NI) study protocol is *in italic*.

Atrial fibrillation (AF) is characterized by a rapid, irregular heartbeat which can cause blood to pool in the atria and increase the risk of the formation of blood clots. AF affects 0.6% to 1.6% of the general population and up to 14% in cardiovascular clinics in Japan¹⁻³. AF can be categorized into three main categories based on patient characteristics: lone atrial fibrillation – AF in the absence of overt cardiovascular disease or precipitating illness⁹; non-valvular AF (NVAF) – presence of AF without concurrent rheumatic mitral valve disease or history of mitral valve repair or prosthetic heart valve; and secondary AF-AF that occurs in the setting of acute myocardial infarction (MI), cardiac surgery, pericarditis, myocarditis, hyperthyroidism, pulmonary embolism, pneumonia, or other acute pulmonary disease. Anticoagulation therapy is important to prevent thromboembolism in patients with NVAF. Warfarin, a vitamin K antagonist, is the first oral anticoagulant approved for the treatment and prevention of thromboembolism in Japan in 1962 and it had long been the only oral anticoagulant until the first non-vitamin K antagonist oral anticoagulants (NOACs), dabigatran, was introduced with approval for NVAF treatment in March 2011, followed by rivaroxaban in January 2012, apixaban in December 2012, and edoxaban in September 2014 in Japan.

Although randomized control trials (RCTs) aimed at head-to-head comparison with placebo or a reference drug may provide evidence of safety and efficacy of treatments at the highest level, there are potential limitations derived from a limited number of pre-selected patients and strict patient eligibility criteria with regard to age, comorbidities, and concomitant medications. Accordingly, these studies may not accurately represent what happens when drugs are used in general clinical practice. Recently, in order to overcome the drawbacks of RCTs and corroborate the evidence from RCTs, real-world evaluations of drugs have been conducted. As for anticoagulants, there are some studies that have evaluated safety and effectiveness of NOACs such as apixaban, dabigatran, and rivaroxaban in the real-world setting and the results were similar to those obtained from RCTs⁴⁻⁷. However, these studies are not sufficient, especially for effectiveness evaluation, and real-world data (RWD) specific to each country or region are also required. For example, Asian populations, including Japanese population, are known to be more

prone to intracranial hemorrhage when treated with warfarin¹⁰. Japan is a rapidly aging society with a large proportion of the population aged 75 years or older. Unfortunately, there have been few large-scale, real-world studies to investigate safety and effectiveness of NOACs in patients with NVAF receiving NOACs versus warfarin in Japan.

The objective of this study is to compare the risk of incidence of stroke and bleeding among patients with NVAF newly prescribed any of NOACs (apixaban, dabigatran, edoxaban or rivaroxaban), versus newly prescribed warfarin using a nation-wide administrative claims database.

This retrospective study is conducted voluntarily by Pfizer. This study will not be conducted as post-authorization safety study (PASS) [REDACTED] according to the decision by the business process owner [REDACTED].

3 STUDY DESIGN

This is a retrospective observational study using data from the MDV database (data set from March 1st, 2011 to December 31st, 2017). Among patients registered in the database patients are selected based on the inclusion and exclusion criteria (see below). The first observed prescription of apixaban, dabigatran, edoxaban, rivaroxaban or warfarin is used to identify the patient's index date (date of the first prescription of any OACs is defined as "index date") and treatment cohort. Study measures include: (1) for safety evaluation: major bleeding and any bleeding; (2) for effectiveness evaluation: a composite of ischemic stroke, hemorrhagic stroke or SE. The follow-up period is variable, and will begin on the next day of the index date and continue until the earliest of the following scenarios – occurrence of target outcome event (details available in Section 8.2); discontinuation of the index OAC; switching from the index OAC; withdrawal from the database.

4 STUDY POPULATION

Japanese OAC treatment-naïve NVAF patients with who were prescribed apixaban, dabigatran, edoxaban, rivaroxaban or warfarin. Further information on patient selection and enrolment and follow-up time periods are included in Subsections 7.2 of the protocol.

4.1 DATA SOURCE

The analysis will be based on administrative data from MDV Co. Ltd., a longitudinal database based on health insurance claims and medical records obtained from the hospitals in which the DPC payment system for utilization of both inpatient and outpatient hospital claims (percentage of inpatients is about 45%). The database provides claims data from 314 hospitals (as of June 2017) using the DPC system for medical service claims (21% of general hospitals but 55% of general beds in Japan is under the DPC system) including approximately 14 million patient data.

Treatment/cohort labels

- Apixaban Cohort: NVAF patients who initiated apixaban on the index date.
- Dabigatran cohort: NVAF patients who initiated dabigatran on the index date.
- Edoxaban Cohort: NVAF patients who initiated edoxaban on the index date.
- Rivaroxaban Cohort: NVAF patients who initiated rivaroxaban on the index date.
- Warfarin Cohort: NVAF patients who initiated warfarin on the index date

4.2 STUDY OBJECTIVES

The research questions:

1. *Are there any differences in the risk of major bleeding and any bleeding between NOACs and warfarin in the general practice settings in Japan?*
2. *Are there any differences in the risk of stroke/systemic embolism between NOACs and warfarin in the general practice settings in Japan?*

The primary objective of the study compare both the risk of stroke/ SE and of bleeding events among patients with NVAF initiating treatment with one of NOACs (apixaban, dabigatran, edoxaban or rivaroxaban) versus warfarin.

The secondary objectives are

1. *to compare the risk of major GI bleeding, any GI bleeding, and intracranial Hemorrhage between warfarin-initiators and NOAC-initiators*
2. *to compare the risk of ischemic stroke, hemorrhagic stroke or SE between warfarin-initiators and NOAC-initiators*

CCI

CCI

CCI

5 INTERIM ANALYSES

Not applicable.

6 HYPOTHESES AND DECISION RULES

6.1 STATISTICAL HYPOTHESES

This study includes specific hypotheses to be tested. The null hypothesis for each objective is as follows:

Null: The risks of each of the following endpoints do not differ between NVAF patients treated with warfarin and patients treated with apixaban, dabigatran, edoxaban or rivaroxaban.

- Major Bleeding
- Composite of ischemic stroke, hemorrhagic stroke and systemic embolism
- Any bleeding

6.2 STATISTICAL DECISION RULES

All statistical tests will be performed at $p=0.05$ (two-sided) with no adjustment for multiplicity.

Based on results of Japanese sub-population in confirmatory trials for NOACs, the required sample size to detect a significant difference in stroke/SE was calculated. The following sample size calculation is based on the significance level of 0.05 (two-sided) and power of 80%.

Desired Power	Hazard Ratio	Event Rate (Control)	Required Sample Size per Group
0.8	0.6	1.2 %/year	3,166
		1.6 %/year	2,378
		2.1 %/year	1,815
		2.6 %/year	1,469

Desired Power	Hazard Ratio	Event Rate (Control)	Required Sample Size per Group
	0.7	1.2 %/year	6,083
		1.6 %/year	4,570
		2.1 %/year	3,488
		2.6 %/year	2,823
	0.8	1.2 %/year	14,683
		1.6 %/year	11,031
		2.1 %/year	8,422
		2.6 %/year	6,817

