7.2. Setting

This study uses data from the MDV database, which includes the data used for both inpatient and outpatient insurance claims by hospitals according to the Diagnosis Procedure Combination (DPC) procedure.

The study population will consist of adults with NVAF who are newly prescribed apixaban, dabigatran, edoxaban, rivaroxaban or warfarin. Follow-up time period starts from the next day of the index date, and ends depending on following outcomes which observed first.

1. Major bleeding when the target outcome for the analysis is major bleeding.
2. Composite of (ischemic or hemorrhagic) stroke and SE when the target outcome for the analysis is the composite endpoint.
3. Any bleeding when the target outcome for the analysis is any bleeding.
4. Discontinuation of the index OAC: The index treatment will be considered to be "discontinued" if the index OAC is not prescribed within 45 days after prescription refill date (calculated from the last refill date plus days of supply) of the index OAC, even though the patient has >1 medical encounter records after more than 45 days following the prescription refill date. The supposed prescription refill date is regarded as the last day of the follow-up for discontinued patients.
5. Switching from the index OAC: The index treatment is regarded as "switched" if non-index OAC is prescribed within 45 days after prescription refill date of the index OAC when the patient has 1> medical encounter records after more than 45 days following the prescription refill date. The switched day is regarded as the last day of the follow-up for the switched patients.

<Eliquis>

<B0661120> Safety and effectiveness evaluation of patients with non-valvular atrial fibrillation treated with

OACs: Comparison between NOACs and warfarin (CER3)

<Final ver.1.1><20180508>

6. Withdrawal from the database: The patients are regarded as “withdrawal” from the database if the index OAC is not prescribed within 45 days after prescription refill date of the index OAC and there is no data of the patient on the database after prescription refill date. The last medical encounter is regard as the last day of the follow-up for patients withdrawn from the database.

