10.1.3 Analysis of Time-to-Event Data

Time-to-endpoints will be summarized by OAC with the number and percentage of patients with event, and event rates. Event rates will be calculated as the number of patients with event per 100 patient-years at risk. In addition, total patient-years will be presented for each OAC.

Patients who experience a clinical endpoint event after the earlier of their discontinuation of the index OAC, switching from the index OAC, withdrawal from the database, or the end of intended follow-up period (i.e., two years after the index date as primary and one year for a sensitive analysis) will be censored.

Patients who do not experience a clinical endpoint event will be censored at the earlier of their discontinuation of the index OAC, switching from the index OAC or withdrawal from the database will be censored.

Propensity score matching

See above

Cox proportional hazards model

Cox proportional hazards model will be used to compare endpoints in each of the propensity-score-matched cohorts, with robust sandwich estimates to account for the clustering within matched sets. The Cox proportional hazards model will include only index OAC treatment as the independent variable if patient characteristics are balanced between groups based on standardized difference in components of the PS. If not balanced, the unbalanced variable will be also included to the model in addition to the index OAC treatment. The hazard ratios with corresponding 95% confidence intervals and p-values will be reported.

CCI

Kaplan-Meier Method

For each endpoint, Kaplan-Meier curves will be plotted for the time from the index date to first event by index OAC treatment in each of the propensity-score-matched cohorts. The log-rank test is used for comparison between two curves.

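### The sample sizes in SAP 6.2 assume two full years at risk for every patient with no loss. This is not stated with the table, and if the two-year limit in SAP 10.1.3 applies, those sizes give less than 80% power

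*SAP*

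**What the plan says.** SAP 6.2 introduces its table with "The following sample size calculation is based on the significance level of 0.05 (two-sided) and power of 80" per cent. The table crosses hazard ratios 0.6, 0.7 and 0.8 with control rates of 1.2, 1.6, 2.1 and 2.6% per year and gives a size per group for each of the 12 cells. It states no follow-up time, formula or allowance for loss.

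Follow-up is described elsewhere, and not consistently:

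- SAP 10.1.3, on patients whose event comes late, sets the intended follow-up at "two years after the index date as primary and one year for a sensitive analysis".
- The next sentence of SAP 10.1.3 omits that limit: "Patients who do not experience a clinical endpoint event will be censored at the earlier of their discontinuation of the index OAC", or at switching or withdrawal.
- SAP 3 says "The follow-up period is variable, and will begin on the next day of the index date and continue until the earliest of the following" and lists the outcome, discontinuation, switching and withdrawal, with no two-year limit.
- Protocol 7.2 says "Follow-up time period starts from the next day of the index date, and ends depending on following outcomes which observed first". Its list of end points has no two-year limit either.

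The extract is fixed ("data set from March 1st, 2011 to December 31st, 2017"), and the NOACs entered the market at different times: dabigatran in March 2011, "followed by rivaroxaban in January 2012, apixaban in December 2012, and edoxaban in September 2014 in Japan" (SAP 2).

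Protocol 7.5 uses all eligible patients and refers to the SAP for both the required number and the estimated number per cohort. For the sponsor's previous study it reports that "14,830 patients on warfarin, 16,176 patients on apixaban and 4,438 patients on edoxaban were eligible for the analysis". SAP 10.1.1 specifies 1:1 matching without replacement.

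**The concern.** A rate per year gives a number of patients only once a time at risk is fixed, so the table must contain an unstated follow-up assumption. If that assumption equals the longest time any patient may contribute, the SAP's own censoring rules ensure that it is not met on average.

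What is at stake is the stated 80% for a primary endpoint. A reader who meets a non-significant stroke/SE result will judge it against that figure. The matter is sharpest for edoxaban, the last NOAC to market and the smallest cohort for which Protocol 7.5 gives a count.

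**Working it through.** **Inputs.** From SAP 6.2: two-sided alpha 0.05 (z = 1.960), power 80% (z = 0.842), hazard ratios, control rates r and tabled sizes N. From SAP 10.1.1: 1:1 allocation. From Protocol 7.5: 4,438 edoxaban patients in the previous study.

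**Step 1: reproduce the table.** Total events (Schoenfeld) = 4(1.960 + 0.842)² / (ln HR)² = 120.3, 246.8 and 630.5, rounded up to 121, 247 and 631.

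With every patient at risk for t years, N per group = events / {[1 − (1 − r)^t] + [1 − (1 − r)^(t·HR)]}.

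Example, HR 0.7 and r = 1.6%, t = 2: 1 − 0.984² = 0.031744; 1 − 0.984^1.4 = 0.022328; sum 0.054072; 247 / 0.054072 = 4,568. The table has 4,570.

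| HR | Rate/year | Tabled N | Recomputed, t = 2 |
|---|---|---|---|
| 0.6 | 1.2% | 3,166 | 3,165 |
| 0.6 | 1.6% | 2,378 | 2,377 |
| 0.6 | 2.1% | 1,815 | 1,814 |
| 0.6 | 2.6% | 1,469 | 1,468 |
| 0.7 | 1.2% | 6,083 | 6,082 |
| 0.7 | 1.6% | 4,570 | 4,568 |
| 0.7 | 2.1% | 3,488 | 3,487 |
| 0.7 | 2.6% | 2,823 | 2,822 |
| 0.8 | 1.2% | 14,683 | 14,679 |
| 0.8 | 1.6% | 11,031 | 11,028 |
| 0.8 | 2.1% | 8,422 | 8,420 |
| 0.8 | 2.6% | 6,817 | 6,815 |

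Every cell agrees within 1 to 4 patients. Other standard formulas (exponential or linear event probabilities, Freedman events) imply 1.97 to 2.10 years. One year would need about twice the tabled sizes and three years about two thirds, so neither fits.

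**Step 2: compare with the censoring rules.** Under a two-year limit no patient contributes more than 2.0 years. Discontinuation, switching and withdrawal shorten this, and so does the end of data for anyone indexed after 31 December 2015. For edoxaban, available from September 2014, that is the last 24 of 40 calendar months. The mean is therefore below 2.0 years.

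**Step 3: power at the tabled N for a shorter mean time t (assumed values).** E = N × {[1 − (1 − r)^t] + [1 − (1 − r)^(t·HR)]}; power = Φ(|ln HR|·√E / 2 − 1.960).

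Example, HR 0.7, 1.6%/year, N = 4,570, t = 1.4: E = 173.7; 0.3567 × 13.18 / 2 − 1.960 = 0.390; power 65.2%.

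| Mean years at risk | Power, range over the 12 cells |
|---|---|
| 2.0 | 80.0–80.3% |
| 1.9 | 78.0–78.3% |
| 1.75 | 74.7–75.0% |
| 1.4 | 65.1–65.5% |
| 1.0 | 51.1–51.5% |

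**Step 4: edoxaban against the table's own sizes.** Take 4,438 as a ceiling on matched pairs. It is below the tabled size for HR 0.7 at 1.2%/year (6,083) and at 1.6%/year (4,570, short by 132 or 3%), and for HR 0.8 at every rate (6,817 to 14,683): 6 of 12 cells. Power with 4,438 pairs and the full two years, over the tabled rates:

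| HR | Expected events | Power |
|---|---|---|
| 0.6 | 169.7–365.9 | 91.4–99.8% |
| 0.7 | 180.3–388.5 | 66.8–94.0% |
| 0.8 | 190.8–411.0 | 33.8–61.9% |

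Exponential event probabilities lower the bottom of the HR 0.7 range to about 66%.

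**The case against.** The strongest reply is that the table decides nothing. The data are a fixed retrospective extract, all eligible patients are used, and no recruitment or stopping decision rests on 6.2. Hazard ratios are reported with 95% confidence intervals, so an imprecise edoxaban result would be visible. The two-year figure is also in the SAP, in 10.1.3. All of this stands and limits the consequence. It does not make the stated 80% right: 10.1.3 supplies the two years as a maximum, while the table uses them as every patient's time at risk.

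Four stronger readings are tempting, and the documents do not support them.

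- A reader might infer that the four comparisons have 65% or 51% power. Those figures apply at the tabled N only. For apixaban, for example, the previous study's counts allow up to 14,830 pairs, above the largest tabled size of 14,683.
- A reader might infer that the one-year sensitivity analysis has at most about 51% power. That too holds only at the tabled N.
- A reader might infer that without the two-year limit the table holds for the three NOACs that were launched earlier and fails for edoxaban. This depends on the shape of the index dates. With no limit and no loss, an assumed linear rise in uptake gives apixaban 72–73% and rivaroxaban 79–80% at the tabled N; an assumed linear fall gives edoxaban 83–84%. The documents give neither index dates nor persistence.
- A reader might infer that the cohort estimates are absent from the whole SAP. Parts of it are redacted; one can say only that 6.2 does not show them.

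**Conclusion.** The point holds. The 12 sizes rest on an unstated assumption of two full years at risk with no loss. If the two-year limit in SAP 10.1.3 applies to all patients, the tabled sizes give less than the stated 80%. That direction needs no outside figure. The amount of the shortfall is conditional on a mean time at risk that the documents do not give. If the limit does not apply, the documents do not settle whether the table holds for a given NOAC.

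Separately, if 4,438 is a ceiling on pairs, the matched edoxaban comparison misses half of the tabled sizes even at two full years. It is well powered for HR 0.6, mixed for HR 0.7 and weak for HR 0.8, and SAP 6.2 does not say so. The ceiling is an assumption taken from the previous study, and it does not bind the secondary IPTW analysis, which is not restricted to pairs.

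Estimates and tests do not depend on the table. This is a correction to a stated figure, not a flaw in the analysis.

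**What to change.** In SAP 6.2:

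- State the two-year, no-loss assumption and the formula.
- Restate the requirement as events (121, 247 and 631 for HR 0.6, 0.7 and 0.8) or as person-years per group. From events / [r(1 + HR)], these are about 2,900–6,300, 5,600–12,100 and 13,500–29,200 over the tabled rates.
- Show power at the tabled sizes over a stated range of mean on-treatment time below two years.
- Add the expected number per cohort that Protocol 7.5 refers to, and note which tabled sizes the matched edoxaban comparison is not expected to reach.

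Make both sentences of SAP 10.1.3, SAP 3 and Protocol 7.2 agree on whether the two-year limit applies to all patients.

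The cost is wording and a short recalculation. No extra patients are needed; the only downside is a less favourable stated power.
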